Reducing Perioperative S. aureus Transmission via use of an Evidence-Based, Multimodal Program Driven by an Innovative Software Platform (OR PathTrac)

PI: [name]
IRB ID #: 201802843

9/20/2018

Project Details

I. Project Introduction

- I.1 ***Project to be reviewed by:***
IRB-01
- I.2 ***Project Title:***
Reducing Perioperative S. aureus Transmission via use of an Evidence-Based, Multimodal Program Driven by an Innovative Software Platform (OR PathTrac)
- I.3 ***Short Title (optional):***
- I.4 ***Provide a short summary of the purpose and procedures of the study proposed in this IRB application.***
- ***DO NOT include information on studies not proposed in this application.***
 - ***Use LAY terminology only. This must be easily understandable by IRB community members and nonscientists.***
 - ***DO NOT cut and paste technical abstracts from funding applications that may not be understood by a general audience.***

The purpose of this study is to prevent the spread of S. aureus, a dangerous bacterium, within the operating room and between patients undergoing surgery. We will combine several approaches in a "bundle" of activities to achieve this goal. The bundle will include removal of bacterial pathogens from patient skin sites before surgery, from provider hands before, during, and after surgery, from environmental surfaces before and after terminal cleaning, and from the injection ports of patient intravenous catheters. We will use a new surveillance system to evaluate how well the bundle, and each component of the bundle, is working. Surveillance will identify S. aureus transmission events, and movement of S. aureus between reservoirs before, during, and after surgery (perioperative). Surveillance will map transmission events to identify actionable steps to improve the bundle. An infection control perioperative team will act on the surveillance reports to proactively address the action items, and to measure the effect of their efforts for the treatment group. We will compare perioperative S. aureus transmission events for patients receiving the bundle to perioperative S. aureus transmission events for patients receiving usual care.

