Preoperative swab kit orders will track informed, written consent and will populate a list in EPIC for the PI ([name]) that will be sorted by type of surgery and filtered (at the top of the list) by patients with orders for the kit that are actually booked for surgery within 10 days of the current date. That list will be used by [name] to send kits to patients for preoperative swabbing and if in the treatment group, decolonization with Povidone iodine. Before sending, a new signed and held POC preoperative swab kit order will be placed and associated with the kit number. The kits will be sent by the research team to the patient along with a prepaid mailer. The kit will include 3 swabs (nasal, axillary, and groin), preprinted instructions for use, and an insert briefly summarizing the study for a reminder (see attached documents). The patient will follow the kit instructions and send the kit to RDB for processing.

RDB will process the samples and enter the results into the software platform. RDB will send a list of kit numbers received to [name]. [name] will complete the signed and held order in EPIC for those received. This will create an ICON indicating complete. The complete ICON will guide OR PathTrac Surveillance, where a treatment and control patient are selected each day, as geographically dispersed as possible in the OR.

Patients in treatment lines with completed orders who are selected for surveillance will receive the treatment bundle (see below). Patients in usual care lines with completed orders who are selected for surveillance will receive usual care. All second patients in the observational pairs described below will receive usual care. Only the first patient in a treatment pair will receive the bundle (The goal is to examine the impact of an evidence-based bundle in preventing spread of bacteria from one patient to another).

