- Biologic samples (blood draws, check swabs, saliva samples, tissue samples, etc.) - We will use IATA methods for bacterial transport/transfer. Patient swab samples will be stored and identified solely by the kit identification number used to obtain the swab. In the event that a patient subsequently develops an infection, patient cultures will be managed initially by the UIHC clinical lab in accordance with usual care. In addition, samples will later be transferred to RDB Bioinformatics. It is planned that long term storage of biological materials will be with RDB Bioinformatics at UI Bioventures.
 - Name - [name]
 - Title - Associate Professor
 - University Job Classification - FS12

X.5 *Do the confidentiality protections indicated above allow only members of the research team to access the data/specimens?*

No

X.6 *Describe*

RDB Bioinformatics is at UI Bioventures. Bacterial cultures will be de-identified (barcode) and demographic data linked to the barcode. Only bacterial culture data, OR date, surgical duration, OR room and case number, and kit numbers will be shared with RDB.

X.7 *Does your study meet the NIH criteria for a [Certificate of Confidentiality](#) or will you be applying for Certificate of Confidentiality?*

No

XI. Data Analysis

XI.1 *Describe the analysis methods you will use, including, if applicable, the variables you will analyze*

Enrollment/Randomization: Randomization is by the surgical line to treatment or control. The treatment bundle will include the improved RDB Bioinformatics S. aureus decolonization and screening processes described as above, as well as the previously described hand hygiene, environmental cleaning, and vascular care interventions. Active surveillance of bacterial transmission in the perioperative setting for both bundle and usual care groups will be used to drive activities that should further reduce the incidence of bacterial transmission. We will not disrupt processes that are already in place, and results will be entered into the medical record via standard laboratory resulting processes.

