Kits will be transported to RDB Bioinformatics laboratory for processing following sample acquisition. The dynamic surveillance software platform will guide proven, systematic phenotypic and genomic processing of collected samples in order to identify clonal transmission events occurring within and between operating room reservoirs in the observational unit (case pair). Guidance will be based on the strength of epidemiological-relatedness as follows: A transmission event will be defined as the presence of one or more isolates in a measured reservoir that was not present at case start. Transmission events within an observational unit will be further analyzed as directed by the RDB platform to identify clonally-related *S. aureus* transmission events.

The RDB Bioinformatics software platform will process transmission dynamics in order to continually summarize the epidemiology of *S. aureus* transmission. This information will be continually displayed in order to identify the most common reservoir of origin, the most common transmission locations (vectors), the most common mode of transmission (vertical or horizontal), and involvement of key portals of entry (stopcocks). To address strain characteristics, reports will focus on more pathogenic strains defined by the top 5 most transmissible, resistant, and virulent strain characteristics.

Automated analysis reports for overall transmission and for transmission of more pathogenic strains will be used by the infection control perioperative team to continually optimize the interventions affecting all patients in the treatment clusters as described further below. The platform will automatically quantify transmission events occurring in

treatment and control clusters such that involved in data collection and data entry will be blinded to the primary outcome.

All data will be analyzed by the statistician ([name]) at Dartmouth Hitchcock Medical Center who will not be involved in data collection.

Work flow: Monday-Friday only. Limited to patients that are seen in UIHC clinics. 1,000 case pairs: (500 treatment and 500 usual care) will be studied during the 2-year study period. This corresponds to one case pair in the “bundle” group and one case pair in the usual care group each day (5 days a week for 50 weeks each year). All patients will be followed for 90 days for infection development.

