Reducing Perioperative S. aureus Transmission via use of an Evidence-Based, Multimodal Program Driven by an Innovative Software Platform (OR PathTrac)

9/20/2018

Statistical Analysis

Multiple statistical methods were used. For simplification, we list the statistical methods in the precise sequence they are reported in the results.

The Fisher exact test was used to compare patient and procedural demographic information for treatment vs control groups and for cases involving *S* aureus transmission. Similarly, the distribution of patients by ASA scores greater than 2 and by sex for enrolled vs eligible patients were compared by surgeon using the Mantel-Haenszel test.

The Fisher exact test was also used to examine the potential association of each of the covariates mentioned earlier with *S aureus* transmission. None were associated.

A 2-sided Wilcoxon-Mann-Whitney test was used to examine the association of treatment assignment with the number of transmitted *S aureus* isolates. Poisson regression was used to estimate the incidence risk ratio (IRR) of *S aureus* transmission for the independent variable of treatment. Poisson regression was used to estimate the IRR because the incidence of transmission was so large (ie, much greater than 10%) that the odds ratio estimated using logistic regression would be a biased estimator of the relative risk.²⁴ We repeated the analysis using multilevel Poisson regression clustering by surgeon or specialty.

The Fisher exact test was used to compare the proportion of patients in the treatment group with transmission events before vs after surveillance feedback and the proportion of patients with SSI with and without documented *S aureus* transmission. Poisson regression was used to compare the proportion of patients with SSI with and without documented *S aureus* transmission, clustered by surgeon.

The proportion of patients with SSIs was compared with the Fisher exact test. Time to infection was evaluated by Cox proportional hazard modeling. We repeated the analysis using multilevel Poisson regression clustering by surgeon and specialty.

There were no missing data for the primary and secondary outcomes. Calculations were performed using Stata version 16.1 (StataCorp). All P values were 2-sided, and P < .05 was taken to indicate statistical significance.

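### The before-after test of surveillance feedback uses the treatment arm alone, so it cannot separate feedback from a trend shared by both arms; the randomized comparison does not depend on it

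*SAP*

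**What the plan says.** The SAP (Statistical Analysis) gives this test for feedback: "The Fisher exact test was used to compare the proportion of patients in the treatment group with transmission events before vs after surveillance feedback". No control-arm counterpart, time term or clustered repeat is listed for it. For the main transmission analysis, by contrast, the SAP adds: "We repeated the analysis using multilevel Poisson regression clustering by surgeon or specialty". One general rule covers every test: "All P values were 2-sided, and P < .05 was taken to indicate statistical significance".

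The protocol explains why feedback is of interest. Section I.4 says that the infection control team will act on the surveillance reports "and to measure the effect of their efforts for the treatment group". Section XI.1 says that the automated reports will be used "to continually optimize the interventions affecting all patients in the treatment clusters as described further below".

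Both arms are observed at the same time. Under VII.E.6, "a treatment and control patient are selected each day". The work flow in XI.1 plans one bundle pair and "one case pair in the usual care group each day". XI.1 also says that surveillance "for both bundle and usual care groups will be used to drive activities that should further reduce the incidence of bacterial transmission".

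**The concern.** A before-after comparison in one arm attributes to the dividing event whatever else changed over the same period. Over two years that could include season, staffing, case mix or hospital-wide infection control. If transmission fell in both arms for such a reason, the test could give P < .05 with no feedback effect. A shared rise could hide a real effect. The data that would show a shared change are collected in the usual-care arm but do not enter this test.

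An effect reading is foreseeable, because section I.4 speaks of measuring the effect of the team's efforts and the SAP applies a significance threshold to all P values. What is at stake is inference about feedback, not the trial's main result.

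**Working it through.** **1. Inputs from the documents.** Protocol XI.2 (Initial Power Analysis) gives 500 patients per arm and two pairs of planning rates: 40% down to 28%, and 10.58% (58/548) down to 7.41%. The SAP gives a two-sided 5% level. It also describes the incidence as far above 10%, which is closer to the 28-40% pair, but which rate applies here is an assumption.

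**2. Reproducing the plan's own figure.** The documents give no figure for the before-after test. For the randomized comparison with no variation between lines, XI.2 states 98% power. With 40% v 28% and 500 per arm:
- pooled rate 0.34, null SE = √(2 × 0.34 × 0.66 / 500) = 0.02996
- alternative SE = √((0.40 × 0.60 + 0.28 × 0.72) / 500) = 0.0297
- power = Φ((0.12 − 1.96 × 0.02996) / 0.0297) = 0.980, which agrees.

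**3. Assumptions not in the documents.** One outcome per treated pair, 250 before and 250 after, independent patients, no feedback effect, and the same proportional change in both arms.

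**4. The SAP's test under a shared fall.** The rejection probability is the sum, over all pairs (a, b) with Fisher P < .05, of Bin(a; 250, p) × Bin(b; 250, p × RR). Starting from 28%, a 20% relative fall means 70/250 expected before and 56/250 after. Exact enumeration gives:

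| Starting rate | No trend | 10% fall | 20% fall | 30% fall |
|---|---|---|---|---|
| 28% | 4.0% | 9.1% | 26.7% | 55.8% |
| 40% | 4.0% | 12.9% | 42.5% | 78.6% |
| 10.58% | 3.6% | 5.0% | 9.9% | 19.4% |
| 7.41% | 3.5% | 4.4% | 7.5% | 13.5% |

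With a 125/375 split, the figures from 28% are 4.3, 8.6, 22.8 and 46.9%.

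**5. The opposite direction.** With a true feedback RR of 0.7 from 28%, power is 55.8% with no trend. It falls to 34.6% with a shared 10% rise and 18.0% with a shared 20% rise.

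**6. Adding the control arm.** The contrast is ln(RR treatment) − ln(RR control), where each RR is after/before and each arm-period contributes variance (1 − p)/(np). With treatment at 28%, control at 40% and 250 per arm-period:
- Under the same proportional falls it rejects in about 5% of simulated trials.
- If both arms instead fall by the same 5, 8 or 10 points, it rejects in about 6, 8.5 and 11%, so it is not immune.
- Power at a feedback RR of 0.7: SE = √(0.72/70 + 0.804/49 + 2 × 0.6/100) = 0.197; 0.357/0.197 = 1.81; Φ(1.81 − 1.96) = 0.44. That is 44%, against 56% for the one-arm test.
- If a quarter or half of the log effect reaches controls, power is about 27% or 14%.

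**7. Lines that drift differently.** Assume a line-by-period logit SD of 0.2, with the between-line SD of 0.20 from XI.2. The robust contrast without clustering is then falsely significant in about 9-10% of trials with 5 + 5 equal lines and 12-13% with 3 + 3. The one-arm Fisher test ignores the same variation: 8% and 11% with no shared trend, 29% and 31% with a 20% shared fall. A multilevel Poisson version was not simulated. No figure is given for unequal lines, because the documents do not say how patients divide among lines within each arm.

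**The case against.** The strongest reply is that this is an ancillary test. Section I.5 names only transmission and surgical site infection as objectives. The wording in I.4 can be read as plan-do-study-act monitoring by the team itself, and the P < .05 sentence is a general rule. No trend is documented, and with independent patients and no trend the Fisher test holds its level. All of this stands and keeps the point small. It does not give the test a way to tell the two explanations apart.

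The control arm is also not a clean comparator. Under VII.E.6, cleaning feedback goes to affected operating rooms, and under VI.13 the providers change day by day, so feedback may reach usual-care patients and pull the contrast toward the null. The protocol describes feedback as daily for cleaning, monthly for catheter care and otherwise continual, so one common start date may not exist. The contrast itself exceeds 5% when a few lines drift differently. These objections stand too. They are reasons not to make an interaction P value the basis for inference, but they do not argue against showing the control-arm data.

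A reader might go further and infer that the plan has no cut date. The SAP refers to text outside the documents available here, so the date may be defined there, and this point does not rely on its absence.

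**Conclusion.** The point holds in a limited form. As specified, the test cannot distinguish a feedback effect from a trend common to both arms, and this follows from its structure without any assumed number. The size is illustrative only: about 27% false significance from a 28% rate and 10% from 10.58% at a shared 20% fall, against about 4% with no trend. The split, the trend, the starting rate and independence are all assumptions.

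Two stronger readings are not supported. One is that the main result is biased. Treatment versus control is tested separately, by Wilcoxon-Mann-Whitney and Poisson regression, and the arms are planned to enrol concurrently, so a shared trend does not bias that comparison. This clears it only of the present concern, not of others such as the small number of randomized lines. The other is that the SAP claims feedback reduced transmission; it specifies a comparison and states no causal conclusion. The consequence is confined to how this secondary result is read.

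**What to change.** 1. Report the treatment-arm before-after numbers and proportions as description, with no significance-based claim that feedback reduced transmission.
2. Beside them, show usual-care numbers and proportions before and after the same date. If feedback began at different times, show both arms by the same calendar periods. Note that room cleaning and shared providers may carry feedback to controls.
3. Optionally, report the arm-by-period ratio of risk ratios with a 95% confidence interval from the Poisson model, with robust variance and allowing for surgeon or specialty clustering, labelled exploratory.

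The cost is one table and, if step 3 is taken, one model term; no new data are needed. The contrast has lower power (about 44% v 56% at RR 0.7 from 28%, before clustering), and its error can exceed 5% if the few lines drift differently. It removes only a shared trend, so learning to use the bundle, which occurs in the treatment arm alone, would stay mixed with feedback. A null contrast would not show that feedback has no effect.

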Specify your research question(s), study aims or hypotheses (do not indicate "see protocol")

Surgical site infections are a subset of healthcare-associated infections (HAIs) that affect 3-5% of all patients undergoing surgery and are associated with a 2-fold increase in patient morbidity and mortality, a 2-fold increase in hospital duration, and a 66% increase in the risk of intensive care unit (ICU) admission (1-4). The Centers for Disease Control (CDC) and the World Health Organization (WHO) consider HAIs as a devastating issue tied to antibiotic resistance and have highlighted three major goals for HAI prevention including the following: 1) Prevention of infections in patients undergoing surgery, 2) Prevention of patient-to-patient bacterial transmission, and 3) improvement in antibiotic stewardship (5-7). These recommendations apply to the perioperative arena where the contribution of intraoperative bacterial reservoirs to bacterial transmission events and postoperative infection development has been confirmed (8-10). Indeed, a multicenter study recently demonstrated that stopcock contamination occurred in 23% of surgical cases, was associated with increased mortality, and was linked by molecular typing to postoperative infection (9). Intraoperative bacterial reservoir isolates have also been directly linked to the causative organism of infection for 30% of 30-day postoperative HAIs. Finally, transmission of S. aureus has been confirmed in up to 39% of surgical cases and has been directly linked to postoperative infection development(11). As such, attenuation of perioperative S. aureus transmission is an important target for HAI reduction. Therefore, our primary objective is to reduce perioperative S. aureus transmission. Our

secondary objective is to examine the impact of reduced *S. aureus* transmission on the incidence of superficial and deep surgical site infections (SSIs).

I.6 ***Background and significance and/or Preliminary studies related to this project. (do not indicate "see protocol")***

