Sample Processing: All samples will be sent to RDB Bioinformatics for processing. Results will be entered into the software. The software will guide testing to identify *S. aureus* transmission events. *S. aureus* transmission events will be processed to identify transmission stories, and transmission stories will be reported in the software platform to guide proactive improvements in the bundle.

Infection Tracking: The patient will be followed for 90 days postoperatively to identify and infection. Initial screening criteria will include an elevated white blood cell count, fever ($T > 38$ degrees), anti-infection order, culture, or office documentation of infection. If one or more criteria are present, the patient will undergo a full chart review to determine if they developed a healthcare-associated infection (HAI) as determined by National Healthcare Safety Network (NHSN) definitions. All patient cultures obtained for infectious workup by the usual healthcare teams will be saved by the clinical microbiology laboratory. Samples will be sent to RDB for analysis in order to determine if the organism was clonally-related to an organism isolated from one or more reservoirs during the perioperative period.

Confounding Factor Analysis: Information from the patient medical record will be collected by the study team: date and time of surgery, diagnosis, ASA status (a system for assessing the fitness of patients before surgery), age, comorbidities (the presence of one or more additional diseases or disorders co-occurring with (that is, concomitant or concurrent with) a primary disease or disorder), surgery type and duration, type of anesthesia provided, operating room number, gender, dirty or infected surgery (yes/no), preoperative location, postoperative location, and duration of anesthesia. Data will password protected and kept in microEMR.

All patients will be called at 90 days (Up to 3 attempts will be made) to determine if they developed an infection.

VII.E.7 *Will you attempt to recontact subjects who are lost to follow-up?*

No - those lost to followup will not be recontacted

VII.E.9 *Will subjects be provided any compensation for participating in this study?*

No

VIII. Risks

VIII.1 *What are the risks to subjects including*

- emotional or psychological

- financial

- legal or social

- physical?

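### The SSI-by-transmission comparison leaves out treatment arm and service line, which introduces a small bias from arm and possibly a larger one from service line

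*SAP*

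**What the plan says.** Protocol section I.5 states that the "secondary objective is to examine the impact of reduced" S. aureus transmission on superficial and deep SSI.

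The SAP has two analyses that relate SSI to observed transmission. One is a Fisher exact test. Its sentence opens "The Fisher exact test was used to compare the proportion of patients in the treatment group", but that restriction belongs to the comparison before and after feedback; the SSI half of the sentence, which compares "the proportion of patients with SSI with and without documented" S. aureus transmission, names no arm. The other is a regression: "Poisson regression was used to compare the proportion of patients with SSI with and without documented" S. aureus "transmission, clustered by surgeon". No arm, service line or patient covariate is named in either. Significance is at 5%: "All P values were 2-sided, and P < .05 was taken to indicate statistical significance".

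Protocol VII.E.6 has a paragraph that opens "Confounding Factor Analysis: Information from the patient medical record will be collected by the study team". It lists ASA status, comorbidities, surgery type and duration, dirty or infected surgery and other items. The only adjustment that Protocol XI.2 plans is for the treatment effect on transmission, and only if there is imbalance. The SAP also reports Fisher tests of covariates against transmission, with the result "None were associated".

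**The concern.** The bundle is designed to reduce transmission. It also contains elements that could reduce SSI without changing measured S. aureus transmission: povidone iodine at the likely incision site, supervised chlorhexidine wipes, and any effect on other organisms. If both happen, patients with transmission come disproportionately from the control arm, where SSI is higher for other reasons. A pooled comparison then shows an association even when transmission does nothing.

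Service line raises the same problem. Lines are the unit of randomization (Protocol VI.13), so line is tied to arm, and both transmission and SSI may differ by type of surgery. At stake is interpretation: a crude risk ratio could be read as support for the chain from bundle to transmission to SSI.

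**Working it through.** **Inputs from the documents.** Transmission 40% in control and 28% in bundle, 500 patients per arm (XI.2). SSI 3% to 5% (I.5). Pilot transmission 28% in orthopedics and 58% in gyn/onc, for possible events not yet confirmed as clonal (XI.2). **Assumed, because the documents do not give them:** the bundle's effect on SSI outside measured transmission, SSI rates by service line, and equal group sizes. Both arms are taken as pooled.

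**The plan's own figure.** The documents give no figure for this comparison. The stated 98% power without line variation uses the same transmission rates. Pooled standard error √(2 × 0.34 × 0.66 / 500) = 0.02996; unpooled √((0.40 × 0.60 + 0.28 × 0.72) / 500) = 0.02972. Power = Φ((0.12 − 1.96 × 0.02996) / 0.02972) = Φ(2.06) = 98.0%. It reproduces.

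**Arm alone, no true transmission effect.**
- With transmission, the bundle share is 0.28/0.68 = 0.412 and the control share 0.588.
- Without transmission, the bundle share is 0.72/1.32 = 0.545 and the control share 0.455.
- With other-route SSI risk ratio r, the crude risk ratio is (0.588 + 0.412r) / (0.455 + 0.545r). The control SSI rate cancels.

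| r (assumed) | Crude risk ratio |
|---|---|
| 0.7 | 0.876/0.836 = 1.05 |
| 0.5 | 0.794/0.727 = 1.09 |
| 0.3 | 0.712/0.618 = 1.15 |
| 0.1 | 0.629/0.509 = 1.24 |

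At r = 0.5 and control SSI 5%, SSI is 3.97% with transmission and 3.64% without. In simulation (2,000 runs per setting) the Fisher test rejected about 5% of the time there, and about 4% to 10% over r = 0.7 to 0.3, control SSI 3% to 7% and N = 1,000 or 2,000. A Mantel-Haenszel risk ratio stratified by arm returned about 1.0.

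**Service line alone, pilot rates.** With transmission, the shares of the 28% and 58% lines are 0.28/0.86 = 0.326 and 0.674. Without, they are 0.72/1.14 = 0.632 and 0.368.

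| SSI in the 28% and 58% lines (assumed) | With v without transmission | Crude risk ratio | Fisher rejection, N = 1,000 / 2,000 |
|---|---|---|---|
| 4%, 6% | 5.35% v 4.74% | 1.13 | 7% / 9% |
| 3%, 7% | 5.70% v 4.47% | 1.27 | 13% / 22% |
| 2%, 8% | 6.05% v 4.21% | 1.44 | 23% / 43% |

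The direction is also assumed. If the line with less transmission had the higher SSI (6% v 4%), the ratio would be 4.65/5.26 = 0.88. With the planning quartile rates of 33% and 46% and SSI of 2% and 8%, it is 5.49/4.68 = 1.17.

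**Does surgeon clustering remove it?** In a second simulation (400 runs, 40 surgeons in 10 lines, line and arm effects together), the risk ratio was about 1.29 with cluster-robust standard errors, 1.20 to 1.24 with a surgeon random intercept, and about 1.01 after adjustment for line. Robust standard errors leave the estimate unchanged; a random intercept absorbs only part. The SAP does not say which is meant for this model. With the line effect alone, the ten-line setting gave 1.16 to 1.19 under robust errors, so 1.44 is an illustration rather than an expected size.

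**Precision.** At 3% to 5%, 1,000 patients give about 30 to 50 SSIs. At a ratio of 1.09, about 36% of the events fall in patients with transmission (0.34 × 3.97 / (0.34 × 3.97 + 0.66 × 3.64)). With 30 events the standard error of the log ratio is √(1/10.8 + 1/19.2) = 0.38, an interval of a factor exp(1.96 × 0.38) = 2.1 each way. With 50 events it is √(1/18 + 1/32) = 0.29, a factor of 1.8.

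**The case against.** **The covariate screen.** A confounder must be associated with the exposure, and the SAP reports no such association for its covariates. A reader might infer that case duration produces a sizeable false link: transmission of 50% v 30% by duration, with assumed SSI of 5% v 3% or 6% v 2%, gives 1.11 or 1.23. The documents do not support that. If duration was among the screened covariates, a 50% v 30% gap at 500 v 500 would have been found with more than 99.9% power. A gap that could escape the screen, such as 38% v 30% (about 76% power), gives only 1.05 to 1.09. What remains is that the SAP does not list the covariates, non-significance does not show absence of association, and arm is expected to change transmission by design.

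**The other SSI analysis.** A reader might infer that the secondary objective rests on this comparison alone. It does not. The SAP's next paragraph compares SSI proportions by Fisher test, models time to infection by Cox regression, and repeats the analysis with multilevel Poisson regression by surgeon and specialty. Read naturally, that is treatment against control and does not depend on observed transmission. The comparison criticised here is supplementary, although it is the one that addresses the transmission-to-SSI link.

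**The size of the other route.** A ratio of 1.09 requires the bundle to halve SSI outside measured transmission. Povidone iodine at the incision site is conditional on the surgical team's approval. Vascular care, credited in VII.E.6 with a number needed to treat of 16, may act largely through stopcock contamination, which is itself sampled. This limits the size but does not remove the route.

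**The pilot rates.** The protocol expects less variation between lines after genomic analysis, so the service-line figures may be too large.

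**Conclusion.** The point holds as a minor one. Arm is left out of a comparison in which it is plausibly a common cause of exposure and outcome. The resulting bias is small: 1.05 to 1.15 under the assumed other-route effects, well inside the sampling error of 30 to 50 events. Service line may matter more, at 1.13 to 1.44 at the pilot rates, but that rests on non-clonal transmission rates and on assumed SSI rates whose direction is unknown. Surgeon clustering does not fully deal with either.

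A reader might go further and infer that any link found will be spurious, or that the SAP asserts causation. Neither follows. The arm bias seldom reaches significance by itself, and the SAP speaks only of comparing proportions; the causal wording is in the protocol's objective.

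**What to change.** Add treatment arm to the Poisson model of SSI on transmission, or report the comparison within each arm. State whether clustering by surgeon means robust standard errors or a random intercept. Add a sensitivity analysis stratified by service line or specialty; if each line lies wholly in one arm, this also compares patients within arm. With about 30 to 50 SSIs per 1,000 patients, keep any further covariates few and name them in advance. List the covariates that were screened against transmission. Describe the result as an association.

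Arm and surgery type are already recorded, so the cost is SAP wording, one re-run and a slightly wider interval.
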